Study Protocol with Statistical Analysis Plan

Study Title: Augmenting Exposure Therapy for Social Anxiety With Transcranial Direct Current Stimulation

NCT03743571

Document Date: Submitted to the IRB on March 26, 2020

Part II Application – Social Behavioral/Education Research

Note the following:

1. A Part I Cover sheet is required for each project submitted in IRBNet; see [Locating the Cover Sheet](#)
2. See IRB policy for submission requirements for new projects for [Full Committee Review](#) or [Expedited Review](#).

PI Responsibilities

1. How will the PI ensure that all study personnel are informed about the research plan and their research-related duties?	 Routine meetings  Regular communication (e.g., email, phone)  Other research staff training, describe:
--	--

Study Sites and Collaborating IRBS

2. List/describe the study sites:	UNR campus only
3. Will this research be reviewed by other IRBs?	 No  Yes (Consider contacting our office for assessment and coordination of single IRB review.)

Selection of Research Participants

4. How many participants (or records) will be enrolled?	200 Number of participants (NOTE: This is for participants enrolled in the in-person portion of the study. However, we expect that many of those who complete the online prescreen may not meet criteria for participating in the full/in-person study or may not wish to schedule in-person lab visits. We therefore expect the number of individuals who complete the online prescreen will be much higher than 200.)
5. What are the participant eligibility inclusion criteria?	

Inclusion criteria:

- 1) Age 18 or older (i.e., adult able to provide consent).
- 2) Identifies as Latino, or non-Latino and Caucasian
- 3) NOT currently receiving in exposure therapy for social anxiety.
- 4) Levels of social anxiety that are sufficiently high, defined as:
 - Reporting a 6 or higher in response to the question "How anxious would you feel giving a formal speech before a live audience?" on a 0 (no anxiety) to 8 (extreme anxiety) scale
 - Reporting a 5 or higher in response to the question "How likely would you be to avoid taking a class that required an oral presentation?" on a 0 (never avoid) to 8 (always avoid) scale

Age, specify: 18 or older

6. What are the participant exclusion criteria?	 N/A, no exclusion criteria Description:
Exclusion criteria: To ensure the safety of all participants using transcranial direct current stimulation (tDCS) participants will be excluded if they:	

 • A) Have ever had a seizure or any other neurological diagnosis • B) Have had a traumatic brain injury (including concussion) within the last year • C) Have any metal in skull (plates, steel sutures, etc.) • D) Are currently taking anti-convulsant, sedative/hypnotic, or antipsychotic medications • E) Are pregnant • F) Have already participated in a tDCS/tACS study on a study day in which they must receive tDCS stimulation 	
7. Justify exclusions based on age, gender, or race:	
Justification:
 
Age: The aim of the study is improving exposure therapy for adults, so participants must be adults, defined as 18 years or older.
 
Race/Ethnicity: The secondary aim of the study is to compare the responses of Latino and non-Latino/Caucasians to ethnicity matched and unmatched public speaking audiences. Therefore we will only include individuals from one of these two racial/ethnic categories.

8. Will the research involve researchers' clients, students, or employees; or persons who are educationally or economically disadvantaged (see IRB policy for inherently influential situations)?	
 No
 
 Yes, specify and describe additional precautions to ensure participants are fully informed and agree voluntarily:
 
Because the PI and CO-PI are actively teaching in the psychology department, it is possible that one or more of their students could enroll to participate in the study. We determined that it would be unfair to these students to exclude them from the study for this reason alone. Although students would be able to sign up for the study via SONA, and we will also recruit by announcements in classes, we will not announce the study in our own classes in order to reduce any potential for perceived coercion.

Recruitment Methods and Materials	

Check here if there are no processes/mechanisms to recruit participants; skip to next section.
 
9. Who will recruit prospective participants?
	

 Recruitment through SONA
 
 PI
 
 Co-investigators
 
 Study coordinator
 
 Research assistants
	

	
Third party, specify and describe the party's relationship to the study population: Other, specify:

10. Describe where, when, and how recruitment will take place:	
 N/A, recruitment exclusively through SONA
 
Description of recruitment process: Participants will be recruited through SONA; we will use our own SONA posting and the posting of an IRB-approved combined prescreen (1490019 [name] Psychology Studies Prescreening Questionnaire). Additionally they will be recruited by brief announcements to small groups such as organizations and classes. Recruitment will also take place with the use of flyers and social media announcements (both are included in the Appendix).

11. What recruitment materials will be used? ⁱⁱ	
 Flyers/advertisements  Emails/letters  Scripts  Slide or computer presentation
 
 SONA post – Our own post as well as the [name] Psychology Studies Prescreening Questionnaire (1490019)  Social media, specify: posts on facebook, craigslist, twitter, etc.  List serves  Other, specify:

--	---

[Assessing Participants for Eligibility](#)

Check here if participants will NOT be assessed for eligibility; [skip](#) to next section.

12. How will researchers confirm participants' eligibility for the research?	Participants will complete a brief pre-screening form via Qualtrics during which they will answer questions related to the study inclusion and exclusion criteria
13. How will researchers inform participants about the process to assess eligibility?	
Pre-screening survey: Participants will see a brief screen at the end of the pre-screening survey that will inform them whether or not they are eligible to participate in the study.
 
Baseline evaluation: After the completion of their baseline evaluation during visit 1 of the study, participants will be informed whether or not they are eligible by the experimenter.

14. What will happen to screening/eligibility data for individuals who are not eligible to participate? ⁱⁱⁱ	These data will be retained alongside with the full dataset for the study. These data need to be retained for scientific purposes (information relates to external validity of the study), so that the PI can

	describe the population that was excluded from the study.
Recruitment Incentives/Payments	
	
Check here if there are no recruitment incentives/payments; skip to next section.
 
15. What types of recruitment incentives/payments will researchers give participants?^{iv}
 
  Credit through SONA 
 — Course credit; equivalent, alternative opportunities must be available  Money; specify amount: up to \$50 (in amazon gift cards) 
 — Raffle or drawing; specify value, and odds of winning: — Other; specify and value:
16. When and how will researchers distribute incentives/payments?	
 SONA credit awarded via standard procedures
 
Description: Participants can elect to receive payment for their participation or SONA credits. 1 SONA credit is provided for completing the pre-screening assessment. 1 SONA credit is provided for every half hour of study participation for in-person visits.
 
Money: No payment in amazon gift cards will be provided for completing the pre-screening assessment. No payment will be provided if the participant is deemed ineligible for study participation at the beginning of study visit 1.
 
SONA credits and Amazon gift card payments across lab visits will be distributed as follows:
 
Prescreening: 1 SONA Credit No amazon gift card offered
 
Completing Visit 1: \$25 Amazon Gift Card or 4 SONA credits
 
Completing Visit 2: \$25 Amazon Gift Card or 2 SONA credits
 
Completing Online Follow-up Survey during Campus Closure: \$10 Amazon Gift Card

	or 2 SONA credits
17. For all incentives/payments, explain why the amount or value is reasonable for the research:	
 SONA credit, standard amounts
 
Explanation:
 
Amazon Gift Card Reimbursement: The full duration of the study is estimated at 3 hours. Therefore, compensation is approximately \$16.67 per hour, which is commensurate with many standard wages.

18. Will participants be required to provide Protected Personally Identifiable Information (PPII) including social security numbers, to receive incentives/payments? ^v	
 No
 
 Yes, specify the PPII required for payment, to whom it will be provided, and how it will be protected during this process:
 
Participants will provide their name and phone number, and email address on their pre-screening intake. Their payment will be linked to their name on the payment log for the purpose of tracking payments in this multi-session study. Furthermore their study ID number will be linked to their name on a master code list, for the purpose of scheduling study visits.
 
Modifications to procedures due to COVID-19 restrictions:
 
One-month follow up surveys will be administered online instead of in person. The participant's email address, provided previously during the prescreening procedure, will be used to send the survey link to the participant. In order to link information back to the ID number, the survey response will be linked to the participant's email address (sent through qualtrics) and they will also report their full name in the survey. This will ensure that we link the appropriate study ID number to the survey response.

Informed Consent Methods/Procedures	
	
Check here if you do not plan to obtain informed consent from participants); skip to the next section. ^{vi}

19. Describe the process for obtaining legally effective informed consent from each participant (i.e., describe when, where, and how each recruit will be told about the research and agree to her/his participation).	
 N/A, research only involves children^{vii}
 
 N/A, research only involves adults with impaired consent capacity and surrogate consent^{viii}

	
Description of informed consent process: Participants will complete an online consent form prior for the prescreening survey.
 
Participants will complete the full informed consent process (for the in-person study visits) at the beginning of their first visit to the laboratory. A research assistant will provide a brief overview of the purpose, risks/benefits, and procedures involved in the study, including stating that participation is completely voluntary. Participants will then be provided with the informed consent document and offered the opportunity to ask any follow up questions prior to signing the informed consent document if they wish to participate in the study.
 
At the second study visit, participants will be verbally reminded of what will be happening on that specific visit, and the experimenter will reiterate that participation in the study is voluntary and that participants may withdraw from the study at any time.
 
Modifications to procedures due to COVID-19 restrictions: For the online follow-up survey used during campus closure, a brief explanation of the modified procedures and the reduced gift card compensation amount will be included in the email with the survey link. Participants will be offered the opportunity to ask questions via email. Additionally, the first page of the survey will be a consent form describing the modified procedures and new gift card compensation amount. Participants can click to consent.

20. Specify which researchers will obtain informed consent from participants:	 For online pre-screening only - Via online or electronic information sheet  PI  Co-investigators  Study coordinator  Research assistants  Other, specify: _____
21. How will researchers ensure consent is obtained in a language understandable to participants?	Check all that apply:  Consent materials reflect the expected literacy of the sample population  Participants speak English  Researcher fluent in participants' language will interpret  Person in community will interpret  Professional interpreter will be present

	
Consent materials translated in participants' language or short-form consent process used Other, specify:

22. How will researchers ensure individuals have sufficient opportunity to consider participation?	
For the online prescreening survey and the follow-up survey (when the campus is closed), participants will have as much time as they need to read the document. For the in person consent process, participants will be informed to take their time in reading over the consent document for the study, and will be invited to ask the experimenters any follow up questions prior to providing consent.

23. How will researchers protect participants from undue influence/coercion during the consent process?	
During the consent process for the in person study visits, experimenters will state that participation in the study is completely voluntary, and that they will not be penalized if they decide not to participate in the study or to withdraw from the study.
 
Modifications to procedures due to COVID-19 restrictions: For the online follow-up survey used during campus closure, participants will be reminded via email and the informed consent page that participation is voluntary, so they may choose to not complete the survey.

24. How will researchers assess each person's comprehension of the research?	
 As recommended by the IRB For the in-person consent: We will ensure comprehension through one-on-one discussion with the researcher/experimenter who is completing the consent process.
 
For the online consent (prescreening and follow-up survey used during campus closure): Participants will have as much time as they need to review the consent form. The consent form will also include contact information for the PI and study coordinators.
 
Other, specify:

Documentation of Consent	
25. Will participants sign an IRB-approved consent form, as required at 45CFR46.117 ?	
 N/A, minimal risk research that is NOT conducted/supported by a federal agency (including the VA); and does NOT involve incomplete disclosure or deception, or prisoners
 
 No, requesting IRB approval to waive requirement for documentation of consent^{ix}
 
 Yes, via short form consent documentation (for non-English-speaking participants)
 
 Yes

Research Costs

26. Will participation result in out of pocket expenses (including costs for cell phones used in research), co-pays, 3 rd party payer costs, or research-related injury costs?*	 No  Yes, complete the following: What costs will participants or 3 rd party cover? What costs will the researchers cover? What costs will the VA cover? What costs will the sponsor cover?
--	--

Study Design/Research Methods

Describe in non-technical terms.

27. What is the background information that supports this research? (Summarize previous work and provide references.)	
Background: About 11% of the general population has social anxiety disorder, which is linked with reduced educational performance and quality of life, and increased rates of substance use, depression, and suicide attempts [1-4]. Furthermore, social anxiety is unlikely to remit without intervention [5], and Latinos with persistent social anxiety report higher levels of overall impairment relative to their white, non-Latino counterparts [6]. Exposure therapy, which involves repeated exposure to feared situations, is one of the most effective treatments for social anxiety [7]. However, even with this top-of-the-line treatment approach, only about 25-50% of patients achieve full remission [8].
 
Transcranial direct current stimulation (tDCS) targeting the medial prefrontal cortex (mPFC) may offer a low-risk and cost-effective pathway to improving outcomes from exposure therapy for social anxiety. Several lines of research point to the importance of mPFC activation in facilitating fear reduction. For example, findings from animal models have demonstrated that electrical stimulation of the mPFC facilitates fear extinction, the primary mechanism of exposure therapy [9]. Moreover, in clinical samples, response to exposure-based therapy for social anxiety is associated with increases in negative connectivity between regions of the mPFC and the amygdala (i.e., mPFC inhibition of limbic-driven emotional distress) [10,11]. tDCS is an especially promising strategy for facilitating mPFC response during therapy. This form of non-invasive neuromodulation is thought to enhance neuroplasticity, particularly after multiple sessions in healthy and clinical populations, with no known serious adverse effects [12]. This present study will therefore examine whether active (versus sham) tDCS targeting the mPFC during exposure therapy facilitates fear reduction in people with social anxiety. This study will also evaluate how two different ethnic/racial groups (Hispanic and non-Hispanic/Caucasian) respond to public speaking audiences that are either 75% matched or 75% unmatched to the participant's own ethnicity.
 
Findings will provide insight into whether tDCS can be used to improve outcomes from exposure therapy for social anxiety, a debilitating disorder that is particularly severe among Latinos. Findings will also provide insight into whether tDCS can be used to facilitate extinction toward more extinction resistant cues (e.g., public speaking audiences that are not matched to the participant's own ethnicity),

---	---

28. State the study purpose, research hypothesis, or research questions:
	
Design: We will recruit participants with a fear of public speaking, the most commonly feared situation among individuals with social anxiety and among the general population [12-14]. Participants will be randomized to receive either active/anodal or sham tDCS stimulation targeting the vmPFC during one, 20 to 30-minute exposure therapy session delivered through virtual reality (VR). VR-based exposure therapy for public speaking anxiety is equally effective as in vivo/in life exposure therapy [8], but allows for greater consistency of the exposure environment between participants (e.g., consistency in listener facial expressions). During exposure therapy, participants will complete six, 3-minute public speaking trials. During each 3-minute public speaking trial, the audience will be comprised of either 75% Latino individuals/25% non-Latino Caucasian individuals, or 75% non-Latino Caucasian individuals/25% Latino individuals (gender of audience members will be equally distributed among each ethnicity group). Order of ethnicity matched and unmatched trials will be randomized.
 
Severity of social anxiety will be assessed at baseline and 1-month follow up with (1) a validated battery of questionnaires (the Personal Report of Public Speaking Anxiety and the Self-Statements during Public Speaking Scale), and (2) two behavioral approach tests (BATs), each involving a short speech in virtual reality to either an ethnicity matched or ethnicity unmatched audience. Fear will be assessed during each BAT behaviorally (total duration of speech out of a 5-min maximum), physiologically (electrodermal response and heart rate variability), and subjectively (peak fear rating on a scale from 0 to 100).
 
Study Aims:
 
Test the hypothesis that augmenting exposure therapy with tDCS facilitates alleviation of social anxiety symptoms. If tDCS targeting the mPFC improves treatment response, we would expect to detect lower symptom scores in the active (versus sham) tDCS group on self-report and BAT measures at 1-month follow-up. If tDCS is ineffective, we anticipate observing no differences in symptom severity between the active and sham tDCS groups at one-month follow-up.
 
Test the hypothesis that pairing exposure therapy with active (vs sham) tDCS facilitates extinction of fear response toward ethnic out-group, public speaking audiences. If tDCS facilitates reduction of fear toward ethnic out-group individuals, we expect an interaction between tDCS group (active vs. sham; between-subjects variable) and public speaking audience (ethnic-matched vs. ethnic-unmatched; within subjects variable) on behavioral, physiological, and subjective indices of fear response during the BATs at one-month follow-up. We expect that the active tDCS group will show equally low fear response on ethnic-matched and ethnic un-matched BATs at one-month follow-up, and the sham tDCS group will show higher fear responding during the ethnic un-matched BAT relative to the ethnic-matched BAT at one-month follow-up.

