	
Before and after exposure therapy, and before and after each behavioral avoidance test (BAT), participants will additionally self-report on their emotional state (e.g., fear levels) and beliefs (e.g., belief that public speaking practices will be/were harmful/negative). During exposure therapy, participant's physiological responding will be recorded (heart rate and electrodermal skin response). After exposure therapy is complete, participants will fill out a question indicating their best guess as to their treatment assignment (placebo or active tDCS). This question is to ensure that blinding was effective.
 
Behavioral avoidance tests (BATs): Participants will be complete two behavioral avoidance tests. The BATs will involve providing two public speeches to an audience in virtual reality that is A) 75% matched to the participant's ethnicity, and b) 75% un-matched to the participant's ethnicity. Participant's responding will be measured subjectively (with self report items), physiologically (with electrodermal skin response and with heart rate), and behaviorally (recording duration eye contact with audience members, and overall duration of the speech). The subjective, physiological, and behavioral measures of anxiety during the behavioral avoidance task provide a triangulated measurement of the construct of public speaking anxiety. The behavioral approach tests will be completed at baseline and 1-month follow up.
 
Modifications to procedures due to COVID-19 restrictions: For the online follow-up survey, only the following questionnaires will be included, due to participants' completing the survey at home: Intergroup Anxiety Scale, Personal Report of Public Speaking Anxiety, Self-Statements During Public Speaking, and a modified MINI – Social Anxiety interview so that participants can answer the questions without the presence of an interviewer. See Appendix- Questionnaires to view interviews that have been modified to questionnaires.

40. How will researchers analyze the data? ^{xvi}	Primary analyses will be ANCOVAs, evaluating the impact of tDCS group (active vs sham) on outcome measures (questionnaires, physiology, and behavior) at post-treatment and follow-up, controlling for baseline levels. The hypothesis is that participants with active (vs sham) tDCS will have

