	
lower symptom scores at post-treatment and follow-up (adjusting for baseline levels).
 
We will also use a repeated-measures ANOVA to examine whether tDCS group (active vs sham; between-subjects variable) interacts with ethnic make-up of the public speaking audience (ethnicity- matched vs. ethnicity-unmatched; within-subjects variable) to determine fear response on each index of fear reactivity (behavioral, physiological, and subjective fear response) at one-month follow-up.

41. Will this research include records of participants' voices or images? ^{xvii}	
 No
 
 Yes, audio; describe and justify:
 
 Yes, video; describe and justify:
 
 Yes, photographs; describe and justify:

Research Risks	

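### Item 7 words the secondary aim as a comparison of two ethnic groups, but the aims section and both planned models carry only tDCS group by audience match, with no participant-ethnicity term

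*Combined protocol and SAP*

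**What the plan says.** Item 7, which justifies exclusions by age, gender or race, states: "The secondary aim of the study is to compare the responses of Latino and non-Latino/Caucasians to ethnicity matched and unmatched public speaking audiences". The next sentence rests the enrolment restriction on that aim: "Therefore we will only include individuals from one of these two racial/ethnic categories". Stimulation is not mentioned there.

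Item 27 (background) is close to item 7 but stops short of saying that the groups are compared: "This study will also evaluate how two different ethnic/racial groups (Hispanic and non-Hispanic/Caucasian) respond to public speaking audiences". The same item also says that the findings will show whether tDCS helps extinction toward more resistant cues, and gives unmatched audiences as the example.

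Item 28 lists two study aims. The second concerns stimulation and audience type: "we expect an interaction between tDCS group (active vs. sham; between-subjects variable) and public speaking audience (ethnic-matched vs. ethnic-unmatched; within subjects variable", assessed on the behavioral approach test (BAT) measures at one month. It does not contrast one group of participants with the other.

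Item 40 gives two models. The first: "Primary analyses will be ANCOVAs, evaluating the impact of tDCS group (active vs sham) on outcome measures", adjusted for baseline. The second is a repeated-measures ANOVA to "examine whether tDCS group (active vs sham; between-subjects variable) interacts with ethnic make-up of the public speaking audience" on each index of fear at one month. Participant ethnicity is in neither. Item 39 names potential moderators (perceived skin tone, intergroup contact, intergroup anxiety), and ethnicity is not among them.

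Ethnicity is nevertheless known for every participant. Inclusion criterion 2 in item 5 reads "Identifies as Latino, or non-Latino and Caucasian", and item 12 says that the eligibility questions are asked at prescreening.

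**The concern.** The aim used to justify restricting enrolment to two ethnic groups is not worded like the aim that is tested. On the between-group reading of item 7, someone following item 40 exactly would finish the analysis without comparing Latino and non-Latino Caucasian participants. Anyone who then wanted that comparison would choose its model and contrast after seeing the data, although the variable is available from the start.

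There is also a point of efficiency. Match is defined relative to the participant's own ethnicity. If one audience is harder for everyone, that effect raises the unmatched-minus-matched score in one ethnic group and lowers it in the other. With no ethnicity term, this spread goes into the error of the planned tDCS by match test.

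**Working it through.** **1. The texts side by side.** Item 7 names two groups of participants and two audience types. Item 28 (second aim) and item 40 (second model) name two tDCS arms and two audience types. Only audience type is common to both.

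**2. Does any item 40 parameter give the between-group comparison?** Code tDCS (T), match (M) and participant ethnicity (E) as ±1 over the eight cells. The repeated-measures model {1, T, M, T×M} has rank 4. Adding any one of E, E×M, E×T or E×T×M raises the rank to 5, so none of them is a function of the planned parameters. On the between-group reading, item 7 is not estimated. On the pooled reading, it is the M main effect, which the model already contains.

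**3. What would E×M mean?** With two groups and two audiences, E×M is the same contrast as which ethnic group forms the audience majority. Suppose the mostly Latino audience is harder by d for everyone. The unmatched-minus-matched score then shifts by +d in non-Latino Caucasian participants and by -d in Latino participants. The groups differ by 2d on this score with no difference in their response to matching.

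**4. Effect on the planned tDCS by match test.** From the documents: N = 200 (item 4) and two arms. Assumed: 100 per arm, two-sided 5% level, no loss, interaction 0.4 SD, Latino share p from 0.5 to 0.2, and d of 0, 0.3 or 0.5. The SD is the within-group SD of the unmatched-minus-matched score. The documents give no power calculation, so there is no planned figure to reproduce.

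Without the ethnicity term, the score variance is 1 + 4p(1-p)d². With it, the variance is 1. The standardized interaction is 0.4/√variance, and power comes from the noncentral t distribution.

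| d | p | Variance without term | Standardized interaction | Power without term | Power with term |
|---|---|---|---|---|---|
| 0.5 | 0.5 | 1 + 4(0.25)(0.25) = 1.25 | 0.358 | 71% | 80% |
| 0.5 | 0.2 | 1 + 4(0.16)(0.25) = 1.16 | 0.371 | 74% | 80% |
| 0.3 | 0.5 | 1 + 4(0.25)(0.09) = 1.09 | 0.383 | 77% | 80% |
| 0.3 | 0.2 | 1 + 4(0.16)(0.09) = 1.058 | 0.389 | 78% | 80% |
| 0 | either | 1 | 0.400 | 80% | 80% |

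In simulation, type I error of the tDCS by match test was 4.5-5.5% with or without the term.

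**5. Precision of the added contrast.** SE = √(1/(Np) + 1/(N(1-p))), and the 95% half-width is 1.96 × SE. At N = 200:
- p = 0.5: SE = √(1/100 + 1/100) = 0.141, half-width 0.28 SD.
- p = 0.2: SE = √(1/40 + 1/160) = 0.177, half-width 0.35 SD.

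N = 200 is an upper limit for the follow-up BATs. Item 39 omits them from the online follow-up used during campus closure, and the documents do not say how many participants that affects.

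**The case against.** The strongest reply is that the operative parts of the plan agree. Item 28 is headed as the study aims and lists two, and item 40 supplies one model for each. Item 7 is a one-sentence answer to a form question about exclusions, and item 27 also carries the tDCS-by-audience purpose. Item 7 can moreover be read as comparing matched with unmatched audiences over everyone enrolled. All of this stands, and it limits the certain defect to one loosely worded sentence.

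It is also fair to say that E×M cannot show that the groups differ in their response to matching (step 3). That stands too, and it is why the contrast should be descriptive. It does not remove the other reason for including the term, which is to take audience-composition variance out of the planned test.

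Four stronger readings are tempting, and the documents do not support them:
- **The trial has lost its secondary aim.** Item 28 states a second aim and item 40 analyzes it.
- **The enrolment restriction is left without a reason.** A design with two audiences, each matched to one of two groups, supports the restriction under either reading of item 7.
- **The planned interaction test is biased.** The arms are randomized, so leaving ethnicity out can cost precision but does not distort the test.
- **Item 27 sets up an ethnic contrast in audience response.** Its sentence that "Latinos with persistent social anxiety report higher levels of overall impairment relative to their white, non-Latino counterparts" concerns overall impairment, not response to audiences.

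**Conclusion.** The point holds in a limited form, and it is minor. Item 7 is out of line with items 28 and 40. Whether that leaves an analysis gap or only a wording fault depends on which reading of item 7 was intended, and the documents do not settle this. No planned result is invalidated.

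The measurable part is the efficiency of the tDCS by match test: up to about nine percentage points of power (71% against 80%) in the least favorable scenario examined, two to three points with a 0.3 SD composition effect, and none with no composition effect. This rests on the assumed 0.4 SD interaction, the assumed composition effects, a Latino share of 20% to 50%, equal arms and no loss. None of these assumptions is given in the documents.

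**What to change.** 1. Reword item 7 to state the same secondary aim as item 28, so that the reason given for the ethnic restriction is the aim that is tested.
2. In either case, add participant ethnicity and ethnicity by audience match to the item 40 repeated-measures model for each BAT index at one-month follow-up. Keep tDCS by match as the planned test.
3. Report ethnicity by match with a 95% confidence interval, labeled descriptive. State that with two groups and two audiences it equals the audience-composition effect, and that it cannot show that the groups differ in their response to matching.

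The cost is small. The variable is already obtained at screening, so no new data or visits are needed. The planned test gives up one degree of freedom, which is negligible at this sample size. Each index gains one imprecise descriptive contrast, with a half-width of about 0.28-0.35 SD at N = 200 and wider if fewer participants complete the follow-up BATs.
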